#### **2.4.6.1.6 Adverse events leading to dose reduction**

Any AEs leading to dose reduction will be listed including the olipudase alfa dose of the infusion prior to or during the occurrence of the AE leading to dose reduction, where applicable.

#### **2.4.6.1.7 Adverse events leading to drug interruption**

Any AEs leading to drug interruption will be listed including the olipudase alfa dose of the infusion prior to or during the occurrence of the AE leading to drug interruption, where applicable.

### **2.4.6.2 Laboratory data**

For parameters that are reported as below the quantification limit (BQL), the results often convey a clinically meaningful change. Therefore, a numerical value is necessary to be imputed for including these in descriptive statistics calculations. For all these parameters either the lower limit of quantification (LLOQ) is available in the database, or the result is reported as <xx. The numeric value for results of BQL will be imputed as LLOQ/2; the numeric value for results reported as <xx will be imputed as xx/2.

In hematology, platelets and hemoglobin are part of efficacy parameters, and have been described under [Section 2.1.4](#). For the rest of hematology parameters, the baseline will be defined the same way ([Section 2.6.1](#)), and any visit which is scheduled to collect two samples pre-infusion for WBC, the average of the two values will be used as pre-infusion value.

Observed values, change from baseline and percent change from baseline to scheduled study time points will be summarized in separate groups of hematology (excluding hemoglobin and platelets which are considered efficacy parameter, hence the analyses have been described in [Section 2.4.5](#)), liver function tests, coagulation, etc. as described in [Section 2.1.5](#) (excluding lipids which have been described as part of efficacy, [Section 2.4.5.7](#)). Summary plots over time will also be provided as needed.

Laboratory values will be classified as normal, above normal, or below normal based on normal ranges when provided by the laboratory. Shifts from baseline to scheduled time points, any time during the on-treatment period and the last available value, in the abnormality of any parameters will be provided.

PCSA values for clinical chemistry, hematology and liver function tests (provided in [Section 7.2](#)) during the study (from first infusion to last available observation) will be summarized. PCSA values for hematology, liver function test and clinical chemistry parameters will be provided in separate listings.

#### **2.4.6.3 Vital signs**

Vital signs will include heart rate (HR, beats/minute), systolic and diastolic blood pressure (SBP/DBP, mmHg), respiratory rate and body temperature (°F or °C). Each vital sign parameter will be summarized as observed parameter value and change from baseline at each scheduled time point.

PCSA values (provided in [Section 7.2](#)) during the study (from first infusion start to last available observation) will be summarized.

#### **2.4.6.4 Electrocardiogram variables**

For ECG parameters, the baseline is defined in [Section 2.6.1](#). The observed data and change from baseline will be summarized at each scheduled time point.

PCSA values (provided in [Section 7.2](#)) will be summarized during the study (from first infusion start to last available observation).

#### **2.4.6.5 Echocardiogram with Doppler**

Shift tables will be created for valve characterization (including aortic regurgitation, mitral regurgitation, pulmonic regurgitation, tricuspid regurgitation). Summary of change from baseline in cardiac index, ejection fraction (%), pulmonary artery systolic pressure will be provided.

#### **2.4.6.6 Physical examinations**

Complete physical examinations will be classified as normal or abnormal. Shifts from baseline to scheduled time points, any time during the on-treatment period and the last available value, in the abnormality of any complete physical examinations (except overall neurological exam - please see [Section 2.4.6.7](#)) will be provided. A listing of the abbreviated physical examination data will be provided.

Observed values and change from baseline for weight, height and BMI will be summarized for all scheduled time points.

#### **2.4.6.7 Extended neurological examinations**

Neurological examinations ([Section 2.1.5.6](#)) will be classified as normal/abnormal findings. Frequency shift table will be provided. The overall evaluation of neurological exam collected in the eCRF under physical exam will be included in this section.

#### **2.4.6.8 Liver biopsy**

Liver biopsy is planned at screening, Week 52 and Week 104. Liver biopsies are evaluated by a Sanofi Genzyme pathologist for liver fibrosis grading and for sphingomyelin accumulation. Fibrosis staging will be performed using the Lathe pathology reports. Liver biopsy report will not be stored in clinical database, but will be received by clinical personnel at the site and kept in the patient local study file. Data of fibrosis staging will be recorded and transferred as external data.

The fibrosis stage will be summarized with number of patients and percentage for each stage at each visit. Cirrhosis and liver failure could be interpreted from this data. Change from baseline in Sphingomyelin accumulation in liver tissue that is assessed from liver biopsy will be summarized under pharmacodynamic endpoints ([Section 2.1.7](#)).

#### **2.4.6.9 Liver function via echo-Doppler ultrasound**

Liver ultrasound Doppler data will be provided in listings.

#### **2.4.6.10 Inflammatory and vascular biomarkers**

Results of inflammatory and vascular biomarkers will be provided in data listings. IL-6 and IL-8 are part of safety biomarkers and will not be included here; for details of IL-6/IL-8 analysis, please refer to [Section 2.4.6.11](#).

#### **2.4.6.11 Safety biomarkers**

Observed values, change from baseline and percent change from baseline will be summarized at each scheduled time point. Summary plot for the mean ceramide levels in plasma over time also be presented. By-patient plots for the observed values over time will be provided for the highly sensitive C-Reactive protein, iron, ferritin, troponin I, calcitonin, Interleukin 6 and Interleukin 8 will be provided.

#### **2.4.6.12 Immune response assessments**

For ADA summaries during PAP period, the baseline is the last non-missing ADA assessment prior to the first IMP. For ADA summaries during PAP+ETP for duration on olipudase alfa exposure, the baseline is the last non-missing ADA assessment prior to the first olipudase alfa infusion.

Data listings will be provided to display results of anti-olipudase IgG antibody, neutralizing antibody, anti-olipudase alfa IgE antibody, serum tryptase activity, complement activation, and skin testing performed. If IgG antibody titer value is reported as <xx, the numeric value will be imputed as xx, the minimum required dilution (MRD), and used for summary purposes. Listing will provide results as reported as well as results as imputed.

A patient with at least one anti-drug antibody (ADA) response available in the database is considered evaluable.

A patient whose ADA status is positive at baseline is considered to have pre-existing ADA.

A patient whose ADA status is positive anytime post-baseline and is negative or missing at baseline is considered to have treatment-induced ADA.

A patient whose ADA status is positive at baseline (pre-existing ADA) and the ADA titer level anytime post-baseline is significantly higher than that at baseline is considered to have treatment-boosted ADA. A difference in titer values between 2 samples representing greater than or equal to twice the dilution level is considered significant. In other words, the post-baseline titer value divided by the baseline titer value will be greater than or equal to 4 to be considered significant. For example, if baseline titer value is 50, the post-baseline titer value has to be  $\geq 200$ .

For patients with treatment-induced ADA, the following 3 ADA responses are defined.

**Transient ADA response** is defined as:

- Treatment-induced ADA detected only at one sampling time point post-baseline (excluding the last sampling time point).
- Treatment-induced ADA detected at two or more sampling time points post-baseline, where the first and the last ADA-positive samples (irrespective of any negative samples in between) are separated by a period of less than 16 weeks, and the subject's last sampling time point is ADA-negative.

**Persistent ADA response** is defined as:

- Treatment-induced ADA detected at two or more sampling time points post-baseline, where the first and the last ADA-positive on-treatment sample (irrespective of any negative samples in between) are separated by at least 16 weeks.
- Treatment-induced ADA detected in the last two sampling time points, irrespective of the time period in between.

The following subclassifications for persistent ADA response will be considered as well. Since this study is ongoing, the final assessment will be the final assessment at the time of data cutoff date for initial BLA submission.

- Low response – if a patient's peak titer  $\leq 400$  and positive at final assessment. This represents the first titer that is greater than a 4-fold increase from the assay minimum required dilution (MRD). Titers within this range would be considered as Low response.
- Intermediate response - if a patient had persistent ADA response but peak titer is  $>400$  and positive at final assessment.
- Tolerized - if a patient had persistent ADA response, but negative at the final assessment.

**Indeterminate ADA response** is defined as:

- Only the last sampling time point is positive and all previous samples are negative.

Pre-existing ADA =  $100 * (\text{Number of patients with pre-existing ADA at baseline}) / \text{number of evaluable patients}$

ADA Incidence =  $100 * (\text{treatment-boosted} + \text{treatment-induced ADA positive patients}) / \text{number of evaluable patients}$

The following information will be provided:

- Number of ADA evaluable patients
- Number (%) of patients with ADA positive/negative at baseline
- Number (%) of patients that never develop ADA at any time (ie, ADA is always negative during baseline and post-baseline visits)
- Number (%) of patients with treatment-boosted ADA
- Number (%) of patients with treatment-induced ADA
- Treatment emergent ADA: Number (%) of patients with treatment-boosted/treatment-induced ADA
- Duration of ADA response: Number (%) of patients with transient/persistent/indeterminate ADA response (each category separately)
- Number (%) of patients within persistent ADA response subclassifications: low response, intermediate response, tolerized (each category separately)
- Patients with treatment-induced ADA will be further characterized
  - Peak ADA titer: Median and 25th/75th quantiles (min, max) of the ADA titer for peak ADA titer of treatment-induced ADA positive patients
  - Last ADA titer (final assessment): Median and 25th/75th quantiles (min, max) of the last ADA titer of treatment induced ADA positive patients
- Number (%) of patients with positive neutralizing antibody (NAb)
  - NAb Inhibition of catalytic activity
  - NAb inhibition of cellular uptake

The assessment of ADA incidence and characterization [REDACTED] will be conducted through pooled analyses and presented in the integrated summary of immunogenicity. The assessment of immunogenicity and safety [REDACTED] will be presented in the integrated summary of safety (ISS).

#### **2.4.6.13 Subgroup analyses for key safety measures in PAP**

The following subgroup analyses for key safety measures will be performed:

- Baseline ALT or AST abnormality (ALT or AST  $\geq 1$  ULN vs ALT and AST  $< 1$  ULN)
- Baseline total bilirubin abnormality (total bilirubin  $\geq 1.5$  ULN vs total bilirubin  $< 1.5$  ULN)

The key safety measures that will be analyzed by the above subgroup include the followings:

- Overview of treatment-emergent adverse events
- Summary of treatment-emergent adverse events by primary SOC and PT
- Summary of protocol-defined infusion-associated reactions by primary SOC and PT

#### **2.4.6.14 PAP+ETP safety analyses**

For categorical measures, such as AE, data throughout both PAP and ETP will be summarized as three groups:

- **Previous placebo group** includes patients who are randomized to placebo. For patients in this group, only the data during olipudase alfa exposure at ETP will be summarized. The baseline will be defined as the last non-missing value prior to first olipudase alfa infusion at ETP.
- **Previous olipudase alfa group** includes patients who are randomized to olipudase alfa. For patients in this group, all the data during PAP and ETP with olipudase alfa exposure will be summarized. The baseline will be defined as the last non-missing value prior to first olipudase alfa infusion at PAP.
- **Overall Olipudase alfa group** includes patients from previous placebo group and Previous Olipudase alfa group.

For continuous measures collected at longitudinal time point, such as labs and vital signs, data throughout both PAP and ETP will be summarized as two groups:

- **Placebo/olipudase alfa group** includes patients who are randomized to placebo. For patients in this group, all data during PAP and ETP will be summarized at each longitudinal time point. The baseline will be defined as the last non-missing value prior to first infusion of IMP at PAP.
- **Olipudase alfa/Olipudase alfa group** includes patients who are randomized to olipudase alfa. For patients in this group, all the data during PAP and ETP with olipudase alfa exposure will be summarized at each longitudinal time point. The baseline will be defined as the last non-missing value prior to first infusion of IMP at PAP.

#### **2.4.7 Analyses of pharmacokinetic and pharmacodynamic variables**

##### **2.4.7.1 Pharmacodynamic analysis**

Pharmacodynamic endpoints include sphingomyelin and its metabolites, including sphingomyelin accumulation in liver tissue. These endpoints will be analyzed using pharmacodynamics population. Observed, change from baseline values and percent change from baseline values will be summarized at scheduled visits. Summary plots of the mean values over time for all pharmacodynamics endpoints will be provided.

### **2.4.7.2 Pharmacokinetic analysis**

Plasma concentration-time data will be analyzed by non-compartmental methods, or nonlinear mixed effects modeling, based upon patient age and data suitability. Values will be reported for individual patient and summarized by dose level, process materials and study week as appropriate.

For ease of presentation, mean values will be arithmetic mean unless specified. Concentration values below the plasma assay limit will be treated as zero in calculating mean values. Mean values below lower limit of quantification (LLOQ) will be reported as LLOQ in the tables and not plotted in the figures if after  $C_{max}$ . Mean calculations and their associated statistics will be generated from unrounded numbers and may differ slightly from those values that would be determined using the rounded numbers displayed in the tables. Values expressed in all tables will be for ease of presentation and will not be meant to imply accuracy to more than 3 significant figures.

Pharmacokinetic parameters of olipudase alfa may be summarized using descriptive statistics such as arithmetic mean, geometric mean, SD, standard error of the mean (SEM), coefficient of variation (CV [%]), minimum, median, maximum, and number of observations for each study visit, and dose level under the responsibility of pharmacokinetics, dynamics and metabolism (PKDM) using WinNonlin Professional, or Phoenix, or NONMEM (VII or above) running on a Linux cluster.

Associations between ADA variables (eg, ADA status) and PK of olipudase alfa (eg, AUC) will be explored for the olipudase alfa treatment group at selected PK visits. If applicable, plot of olipudase alfa PK (eg, AUC) versus the selected PK visit may be provided by ADA classifications for the olipudase alfa treatment group. Nab data may be explored as appropriate.

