1.2.3 Pharmacokinetic sampling during the primary analysis and extension treatment periods

	Before infusion ^a	Midway through	End of infusion	Hours after the infusion ^b						
				1 hour	4 hours	8 hours	24 hours	48 hours	96 hours	168 hours
Study week 2	X	X	X	X	X	X	X	X	X	X
Study week 10	X	X	X	X	X	X	X	X	X	X
Study week 14	X	X	X	X	X	X	X	X	X	X
Study week 26	X	X	X	X	X	X	X	X	X	X
Study week 38	X	X	X	X	X	X	X	X	X	X
Study week 52	X	X	X	X	X	X	X	X	X	X
Study week 54	X	X	X	X	X	X	X	X	X	X
Study week 68	X	X	X	X	X	X	X	X	X	X
Study week 80	X	X	X	X	X	X	X	X	X	X
Study week 132	X	X	X	X	X	X	X	X	X	X
Study week 184	X	X	X	X	X	X	X	X	X	X
Study week 236	X	X	X	X	X	X	X	X	X	X
In case of switch from Process C(■) IMP to the updated manufacturing Process C(■) IMP ^c	X	X	X	X	X	X	X	X	X	X

a Preinfusion sample to be collected within 24 hours before infusion start.

b Sample collections are to be within ±10 minutes for those <8 hours from infusion end and ±3 hours for those ≥8 hours after infusion end.

c For the switch from Process C(■) IMP to the updated manufacturing Process C(■) IMP, samples for PK will be collected at the second dose that is administered after the switch following the same PK sampling schedule

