6 STUDY DESIGN

6.1 DESCRIPTION OF THE PROTOCOL

This Phase 2/3, multicenter, repeat-dose, clinical trial will be divided into 2 consecutive major periods: 1) a randomized placebo-controlled, double-blind primary analysis period (PAP) from Day -60 to Week 52 to be followed by 2) an extension treatment period (ETP). Initially, the ETP will be double-blind as patients in the placebo arm cross over to active treatment.

The PAP will include a screening/baseline period and a treatment period. During the screening/baseline period, from Day -60 to Day 1 preinfusion, approximately 36 patients will provide informed consent and undergo screening assessments to determine trial eligibility and undergo baseline measurements. If all eligibility criteria are met, then patients will be randomized and enter the treatment period on Day 1. Day 1 is the day the first infusion is administered. The visit schedule is calculated using Day 1 of the dose escalation period as the reference. Treatment assignment and randomization will be performed using an Interactive Voice Response System/Interactive Web Response System (IXRS). Patients will be randomly and centrally assigned in a 1:1 ratio across sites using blocks of fixed size into 1 of 2 arms, placebo, saline 0.9% sodium chloride solution, or 3.0 mg/kg olipudase alfa target dose. Dose-escalation during the PAP to the randomized target doses will occur according to the schedule provided in [Section 8.1.3](#) and [Table 1](#). To maintain the double-blind, all patients will dose-escalate using the schedule provided (true dose escalation for patients who were in the placebo arm during the PAP and mock dose escalation for patients in the active arm during the PAP).

After completing the PAP, patients will enter the ETP. Those who were randomized to the active arm will continue receiving the dose to which they were randomized during the PAP (or the highest tolerated dose [HTD], if the randomized dose was intolerable). Patients randomized to the placebo arm in the PAP will cross over to active treatment in the ETP and will undergo dose escalation to a target dose of 3.0 mg/kg olipudase alfa.

Study drug will be defined during the PAP as olipudase alfa or placebo and during the ETP as olipudase alfa and will be administered intravenously once every 2 weeks.

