11.5.6 Pharmacokinetic and pharmacodynamic analyses

11.5.6.1 Pharmacokinetic analyses

Plasma concentration-time data will be analyzed using actual dosing and sampling times by non-compartmental methods.

As data permit, the following PK parameters as specified in [Section 9.3.2.4](#) will be calculated for each patient and each dose of olipudase alfa.

Pharmacokinetic parameters will be assessed as a function of time (upon repeat dosing) and in relation to immunogenicity. If data do not lend to non-compartmental analysis, or for additional analyses, model based approaches such as nonlinear mixed effects modeling may be used.

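### Any mean olipudase alfa concentration below the assay limit is printed as the limit itself, so the group-mean tables cannot show an absence of drug

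*SAP*

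**What the plan says.** SAP 2.4.7.2 gives the handling in two consecutive sentences. The first governs calculation: "Concentration values below the plasma assay limit will be treated as zero in calculating mean values". The second governs display: "Mean values below lower limit of quantification (LLOQ) will be reported as LLOQ in the tables". For figures, the same sentence says such means are "not plotted in the figures if after" Cmax. There is no exception for pre-infusion samples or unexposed patients, no below-limit flag, and no count of quantifiable samples.

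The same paragraph adds: "Mean calculations and their associated statistics will be generated from unrounded numbers". Any SD beside a replaced mean therefore belongs to the calculated mean and not to the printed limit. Results are to be "summarized by dose level, process materials and study week as appropriate".

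Protocol 1.2.3 schedules PK profiles from Week 2 to Week 236, including Week 54, each with a pre-dose draw: "Preinfusion sample to be collected within 24 hours before infusion start". On the placebo arm, Protocol 6.1 states: "Patients randomized to the placebo arm in the PAP will cross over to active treatment in the ETP". It gives the first active dose for those patients as 0.1 mg/kg at Week 54. The PK population in SAP 2.3.3 is mITT patients with evaluable concentrations and is not limited to the active arm.

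**The concern.** A mean is replaced by a number that the data did not produce, and always upwards. If every sample in a cell is below the limit, the calculation gives zero while the table shows a positive concentration equal to the smallest amount the assay can quantify. A reader of the study report cannot tell that cell from one in which patients really had drug at the limit. This matters most in pre-infusion and late samples, where concentrations are lowest. Week 54 is the clearest instance, because the design guarantees zero prior exposure in non-rescued former placebo patients. What is at stake is the accuracy of a descriptive table, not an inference.

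**Working it through.** The SAP states no figure to reproduce here, so the check applies its rules literally. The LLOQ is not given, so everything is in units of the LLOQ.

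**Inputs**
- Below-limit values count as 0 in the mean, and means below the LLOQ are printed as the LLOQ (SAP 2.4.7.2).
- 36 patients randomized 1:1 (SAP 1.3), so about 18 former placebo patients. With the planned 11% non-evaluable, 18 x 0.89 = 16.
- Pre-infusion sample at Week 54 (Protocol 1.2.3); no olipudase alfa before then on placebo unless rescued (Protocol 6.1 and 8.1.6).

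**Formula**
- y = 0 if x < LLOQ, otherwise y = x.
- m = (sum of y) / n.
- Printed mean = m if m >= LLOQ, otherwise LLOQ; that is, max(m, LLOQ).

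**Week 54 pre-infusion, non-rescued former placebo patients**
- All y = 0, so m = 0/18 = 0 (or 0/16 = 0) and the SD is 0.
- Printed mean = max(0, LLOQ) = LLOQ, whatever the LLOQ is.

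**Partly quantifiable cells** (illustrative: n = 18, k values at 2 x LLOQ, the rest below the limit)

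| k | Calculated mean (x LLOQ) | Printed (x LLOQ) | Printed / calculated |
|---|---|---|---|
| 1 | 2/18 = 0.11 | 1.0 | 9 |
| 4 | 8/18 = 0.44 | 1.0 | 2.25 |
| 8 | 16/18 = 0.89 | 1.0 | 1.12 |
| 12 | 24/18 = 1.33 | 1.33 | 1 |

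Overstatement is largest when few values are quantifiable, and it disappears once the calculated mean reaches the limit.

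**How often troughs might be affected**
- The only half-life in the documents is 24 hours, in the contraception rationale of the protocol's amendment history (Appendix C). It is used here as an assumption, with mono-exponential decay.
- Fraction of the end-of-infusion level left: at 11 days 2^-11 = 0.05%, at 14 days 2^-14 = 0.006%, at 17 days 2^-17 = 0.0008%.
- At 14 days a trough is quantifiable only if the end-of-infusion level exceeds the LLOQ by about 16,400-fold (2^14 = 16,384). Trough means below the limit are therefore plausible. Without the LLOQ and Cmax, the number of such cells cannot be determined.

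**The case against.** The strongest reply is that this is a presentation convention with no analytic consequence. Several parts of it stand.

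- A reader might infer that the two sentences contradict each other. They do not: one governs calculation, the next governs display, and both can be carried out in sequence. The fault lies in the value displayed.
- A reader might infer that never-exposed patients are individually reported with drug. SAP 2.4.7.2 also reports values for each patient, and the zero rule applies only when means are formed. Only the group mean is wrong.
- A reader might infer that accumulation or antibody-related loss of exposure would be hidden. Protocol 11.5.6.1 says: "Pharmacokinetic parameters will be assessed as a function of time (upon repeat dosing) and in relation to immunogenicity". Those parameters (Cmax, AUC, CL and the others) come from each patient's concentration-time data and not from tabulated means, and the antibody exploration in SAP 2.4.7.2 names AUC as its example. Trough concentration is not a listed parameter.
- A reader might infer that the printed mean would exceed the maximum in its own row. That holds for an all-below-limit cell only if the row shows a maximum and below-limit values are not displayed there as the limit. The general rule in SAP 2.4 includes a maximum; the list in SAP 2.4.7.2 is optional and written for PK parameters. If a median and maximum are shown, they would also help to expose such a cell.

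It could also be said that LLOQ is shorthand for <LLOQ. The text does not say so, and SAP 2.4.6.2 uses a separate abbreviation, BQL, for laboratory results below the limit. If shorthand was meant, the fix simply states it.

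Finally, a <LLOQ entry also gives one label to every mean between 0 and the limit. That is true, but the label asserts no concentration, and the accompanying count separates an empty cell from a partly quantifiable one.

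**Conclusion.** The point holds as a minor reporting error. Followed literally, SAP 2.4.7.2 makes it impossible for a printed mean concentration to fall below the LLOQ.

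The Week 54 pre-infusion cell of non-rescued former placebo patients is certain to be wrong: calculated 0, printed LLOQ. This assumes that the cell is tabulated by dose level and study week, and that drug-free plasma reads below the limit. Placebo patients rescued before Week 54 are outside this case.

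Other pre-infusion or late cells are overstated whenever their calculated mean is below the LLOQ, by 1.12-fold to 9-fold in the illustrations above. The stronger inference that most pre-infusion rows are affected cannot be verified: it needs the LLOQ and Cmax, and it rests on a half-life quoted for another purpose.

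Individual values, PK parameters, the AUC-based antibody exploration, and efficacy and safety tests are unaffected.

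**What to change.** In SAP 2.4.7.2, replace the table part of the sentence with: *Mean concentrations below LLOQ will be reported as <LLOQ (BQL), with the number of quantifiable values out of n for each cell; the numeric LLOQ will not be substituted for a mean.* BQL is already in the SAP's abbreviation list. Keep the zero rule for calculation and the existing plotting rule.

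The cost is one SAP sentence and a table format change. No new data are needed, and no other analysis changes.
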